16.2.2 Central Laboratory Tests

Refer to the MOP for additional information and detailed instructions.

16.2.2.1 RBC Antibody Testing

Samples will be collected from subjects prior to each study transfusion, at 7 days (\pm 1 day) after each transfusion, at the End of Study Treatment Follow-up Visit, and at the Final Study Follow-up Visit, and held pending antibody screen and identification results from the Local Laboratory. Samples that meet the requirements for shipment to the designated Central Laboratory as noted below will be processed, stored, and shipped according to the instructions specified in the MOP. Samples that do not meet these requirements will be destroyed after study completion according to the Hospital Site's standard procedures.

Requirements for sample shipment: This will be conducted when the crossmatch to MIR RBCs and antibody identification at the Local Laboratory confirms the presence (or suspected presence) of an antibody specific to MIR RBCs, or when the results are inconclusive (eg, positive crossmatch but unidentifiable antibody).

16.2.2.2 HLA Antibody Testing

A central laboratory will conduct HLA antibody testing. Samples will be collected from all subjects prior to each transfusion in Period 1 only, since 1 full treatment period will be adequate to assess chronic transfusions and will incorporate both study treatments (MIR RBCs and REF RBCs). Samples will be processed, stored, and shipped according to the instructions specified in the MOP.

17 CONCOMITANT MEDICATIONS/BLOOD PRODUCTS

All concomitant medications taken from the day of the first study transfusion and throughout the end of study treatment follow-up visit will be captured in the eCRF.

All study related RBC transfusions will be recorded as per Section 14.3.

Additionally, all blood products including off-protocol RBC transfusions, platelets, or plasma transfused until the end of study treatment follow-up visit will be recorded.

No other pathogen reduction treated blood products including platelets and/or plasma may be used for transfusion in subjects until the end of study treatment follow-up visits.

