14.5 Final Study Follow-up

All enrolled subjects will complete a final study follow-up visit, which can be concurrent with routine standard of care, at least 60 days after the last per protocol study transfusion episode.

1. Collect blood for Local Laboratory Tests (Section 16.2.1)
 - a. RBC antibody screen
 - b. If positive, conduct RBC antibody identification and record only new RBC antibodies, if applicable
2. Collect blood for Central Laboratory Tests (Section 16.2.2)
 - a. Collect and hold blood sample for central RBC antibody testing, if applicable. See Section 16.2.2.1 for details regarding criteria for sending samples to the central laboratory
3. Record AEs, SAEs, and UADEs (Section 19)

Table 14-1: Schedule of Procedures for Subjects

	Screening	With Each RBC Transfusion				End of Study Treatment Follow-up/ Early Termination	Final Study Follow-up
	(Days -28 to 0)	Prior to Transfusion	During and Within 15 min Post-Transfusion	1 Day (24 ± 6 hrs) Post-Transfusion ^p	7 Days (± 1 day) Post-Transfusion ^p		≥ 60 days after last transfusion
ICF/assent, ^a and Eligibility	X						
Demographics	X						
Medical/surgical history ^b	X						
Height and weight	X	X ^c					
Randomization	X ^d						
Identify target post-transfusion (15 min) Hb	X						
Record RBC details ^e			X				
Begin transfusion			X ^f				
Calculate the volume of RBCs required to achieve the target Hb		X					
Physical examination ^g	X	X				X	
Vital signs	X	X ^h	X ^h	X			
Routine blood typing and crossmatch, per site standard practice		X					
CBC, plasma free hemoglobin and haptoglobin ⁱ		X	X	X	X	X	
Chemistry		X	Serum K and Na only ^j	X	X	X	
Serum/urine pregnancy test ^k	X	X ^k					
RBC antibody screen and identification ^l		X			X	X	X
Crossmatch with Mirasol-treated RBCs ^m		X			X	X	

	Screening	With Each RBC Transfusion				End of Study Treatment Follow-up/ Early Termination	Final Study Follow-up
	(Days -28 to 0)	Prior to Transfusion	During and Within 15 min Post-Transfusion	1 Day (24 ± 6 hrs) Post-Transfusion ^b	7 Days (± 1 day) Post-Transfusion ^b	2-4 weeks after last transfusion	≥ 60 days after last transfusion
Central RBC antibody screen ⁿ		X			X	X	X
Central HLA antibody screen ^o		X				X	
Central supernatant K, Na and hemoglobin from RBC product		X					
Record concomitant medications		X	X	X	X	X	
Record all blood products, RBC details		X	X	X	X	X	
Record AEs, SAEs, and UADEs		X	X	X	X	X	X

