19.6.1 Recording of Adverse Events

All AEs will be recorded from the time of the first study transfusion through the final follow-up visit or early termination.

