19.9.2 SAE/UADE Reporting

Any SAE/UADE that occurs from the first study transfusion through the final follow-up visit, regardless of relationship to the study treatment or procedures, must be reported within 24 hours of knowledge of the event, and the Sponsor/designee may request additional information from

the Investigator to ensure the timely completion of accurate safety reports. Reporting of the event will occur by submitting a SAE/UADE Form to:

Terumo BCT

Email: [contact]

[contact]

Additionally, the SAE/UADE must be entered on the AE pages of the CRF. Follow-up reports relating to the subject's subsequent medical course after the SAE/UADE must be submitted to the Sponsor/designee and the reviewing IRB/EC, according to the IRB/EC reporting requirements, until either the event has subsided/resolved or until the subject's condition stabilizes and the likely overall clinical outcome has been ascertained (eg, in the case of permanent impairment).

The Sponsor will be responsible for the following:

- Providing all SAE/UADE reports to the independent Data Monitoring Committee (DMC) members upon receipt
- Promptly reporting unanticipated problems involving risk to volunteers or others, SAEs and UADEs related to participation in the study and all volunteer deaths related to participation in the study to the United States Army Medical Research and Materiel Command (USAMRMC)

Office of Research Protections

Human Research Protections Office

(ORP HRPO)

[contact]

[contact]

Email: [contact]

- Follow-up reporting (ie, a complete written report) to the USAMRMC

United States Army Medical Research and Materiel Command

ATTN: MCMR-ZB-PH

[name]

[name]

- Reporting SAE/UADEs to the regulatory authorities in accordance with applicable reporting regulatory guidelines
- Monitoring the safety of the study on an ongoing basis

The investigational site will be responsible for reporting all SAE/UADEs to the following:

- IRB/EC, as required by local policy

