21.9 Safety Analyses

21.9.1 Adverse Events

The Medical Dictionary for Regulatory Activities (MedDRA) version 18.0 or later will be used to code all adverse events to a system organ class (SOC) and a preferred term (PT) within the SOC. The National Cancer Institute Common Terminology Criteria for Adverse Events (version 4.03; CTCAE) will be used to grade severity of all AEs.

The number and percentage of patients reporting each PT will be summarized by the treatment received in the period of onset. Incidence of AEs by maximum reported CTCAE grade will also be tabulated within each arm. The SAEs and AEs leading to study discontinuation will be displayed. The following summaries will be presented:

- Overall TEAEs
- Treatment-related TEAEs
- Adverse transfusion reactions
- TEAEs by maximum CTCAE grade
- SAEs and UADEs
- TEAEs causing discontinuation from the study
- All cause mortality
- Incidence of treatment-emergent antibody with confirmed specificity to RBCs derived from Mirasol-treated WB

Because all AEs will be recorded from the time of the first study related transfusion through the end of study treatment follow-up visit or early termination, any AEs will by definition be TEAEs. However, causation by treatment may not be determined for AEs observed at the final follow-up visit due to off protocol transfusions administered since last study transfusion.

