### **A. Adverse Events**

All subjects will be assessed regularly for potential occurrence of adverse events (AE) from the treatment period until the subject is off study. The Medical Dictionary for Regulatory Activities (MedDRA; Version 16.1) will be used to code all adverse events to a System Organ Class (SOC) and Preferred Term (PT). The incidence of treatment-emergent AEs (TEAE) will be summarized and tabulated by treatment group. A TEAE is defined as any AE that occurs on or after the date of first transfusion.

The National Cancer Institute Common Terminology Criteria for Adverse Events (version 4.03; CTCAE) will be used to grade severity of all AEs. The severity of each AE will be assessed as mild, moderate, severe, life-threatening or fatal. Several occurrences of the same AE in one subject will be counted once and the one with worst severity will be counted.

The relationship of each AE to the study treatment or to study procedure will be grouped as related or unrelated. Any AE with a CRF description of definitely related, probably related, or possibly related will be considered related. Any AE

with a CRF description of not related will be considered unrelated. Several occurrences of the same AE in one subject will be counted once and the one with the closest relationship to study treatment or to study procedure will be counted. If an AE is missing the relationship to study medication, the event will be assumed to be related for analysis and summarization.

The number and percentage of patients reporting each PT will be summarized by the treatment received in the period of onset. Incidence of AEs by maximum reported CTCAE grade will also be tabulated within each arm. The SAEs and AEs leading to study discontinuation will be displayed. The following summaries will be presented:

- Overall summary of TEAEs
- TEAEs by SOC and PT. The number and percentage of subjects with at least one TEAE, as classified by system organ class (SOC) and preferred term (PT), will be summarized by treatment received in the period of onset. For these summaries, subjects with multiple events will be counted only once per SOC and preferred term.
- Study Treatment-related TEAEs by SOC and PT
- Study Procedure-related TEAEs by SOC and PT
- TEAEs by maximum CTCAE grade, SOC and PT
- Serious TEAEs by SOC and PT
- UADEs by SOC and PT
- Adverse transfusion reactions
- TEAEs causing discontinuation from the study
- All-cause mortality

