- Incidence of treatment-emergent antibody with confirmed specificity to RBCs derived from Mirasol-treated WB

Because all AEs will be recorded from the time of the first study-related transfusion through the end of study treatment follow-up visit or early termination, any AEs will by definition be TEAEs. However, causation by treatment may not be determined for AEs observed at the final follow-up visit due to off protocol transfusions administered since last study transfusion

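### AEs are collected to the final visit, but no safety table separates those arising after non-study transfusions, so late events count under the Period 2 product and blur the MIR column

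*Protocol*

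**What the plan says.** **Blood products.** Protocol 17 and SAP VII.C close recording at the EOT visit ("plasma transfused until the end of study treatment follow-up visit will be recorded"). The final-visit list in Protocol 14.5 and the final-visit column of Table 14-1 include AEs, SAEs and UADEs but not blood products.

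**Visits.** Protocol 14.4 puts the EOT visit about 2-4 weeks after the last per-protocol transfusion and before the next standard-of-care one; SAP IV.A says it should coincide with that transfusion. Protocol 14.5 puts the final visit "at least 60 days after the last per protocol study transfusion episode".

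**AE collection.** Protocol 19.6.1: "All AEs will be recorded from the time of the first study transfusion through the final follow-up visit or early termination". Protocol 19.9.2 uses the same window: "Any SAE/UADE that occurs from the first study transfusion through the final follow-up visit".

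**AE analysis.** Protocol 21.9.1 and SAP IX.A give a shorter window, describing recording "through the end of study treatment follow-up visit or early termination, any AEs will by definition be TEAEs". Both then turn to events seen at the final visit and warn that "causation by treatment may not be determined for AEs observed at the final follow-up visit", because of off-protocol transfusions given in the meantime. SAP IX.A also states: "A TEAE is defined as any AE that occurs on or after the date of first transfusion". Patients reporting each preferred term "will be summarized by the treatment received in the period of onset". SAP VI.A defines the start of each period but not the end of Period 2. Under the Safety Set definition in SAP VI.I, a subject who receives any MIR unit in a period counts as MIR for that period.

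**The concern.** The analysis text gets the AE window wrong. It also recognises an attribution problem at the final visit and sets no rule for it. With an open-ended TEAE and no end to Period 2, the tables have only one place for an event arising after the EOT visit: the column of the Period 2 product.

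Subjects in this trial are transfused every 2-4 weeks, so standard-of-care transfusions between the two visits are expected in nearly everyone. In the REF-then-MIR sequence, a reaction to one of them would appear as a MIR reaction. Transfusion-related AEs are a named safety endpoint (Protocol 9). In a safety comparison, dilution towards no difference is the uncomfortable direction. None of the summaries listed in SAP IX.A would let a reader see how much of the MIR column came from this window. SAP IX.F uses time intervals, but only for antibodies.

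**Working it through.** The plan states no figure for this, so the check compares the windows and then works out the schedule.

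**Windows side by side**

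| Item | Ends at | Source |
|---|---|---|
| Blood products | EOT visit | Protocol 17, Table 14-1; SAP VII.C |
| AEs | Final visit or early termination | Protocol 14.5, 19.6.1 |
| SAEs/UADEs | Final visit | Protocol 14.5, 19.9.2 |
| AEs, as described in the analysis text | EOT visit or early termination | Protocol 21.9.1; SAP IX.A |
| TEAE | No end date | SAP IX.A |
| Period 2 | No end date | SAP VI.A |

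The paragraphs that give the shorter AE window go on to discuss final-visit AEs, so the longer window is the operative one.

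**Inputs for the schedule.** The transfusion interval is 14 to 28 days (Protocol 11.2), with a middle value of 365.25/15.6 = 23.4 days from the annual rate cited in Protocol 19.2. Study transfusions in a period are all those in the 50-day wash-in plus the next two. I assume regular intervals, the EOT visit one interval after the last study transfusion, and the final visit at its earliest, 60 days after it.

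Let n be the study transfusions per period and k the non-study transfusions up to day 60 after the last study one. With equal numbers per sequence, the MIR column holds n episodes from Period 1 of one sequence, n from Period 2 of the other, and k late ones. The non-study share is f = k/(2n + k).

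| Interval | n (days) | Late transfusions, days after last study one | EOT to final visit | f |
|---|---|---|---|---|
| 14 d | 6 (0, 14, 28, 42, 56, 70) | 14, 28, 42, 56: k = 4 | 60 - 14 = 46 d | 4/16 = 25% |
| 23.4 d | 5 (0, 23.4, 46.8, 70.2, 93.7) | 23.4, 46.8: k = 2 | 60 - 23.4 = 36.6 d | 2/12 = 16.7% |
| 28 d | 4 (0, 28, 56, 84) | 28, 56: k = 2 | 60 - 28 = 32 d | 2/10 = 20% |

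If the first late transfusion is given at the EOT visit itself, 1 to 3 follow it rather than 2 to 4. A later final visit lengthens the window and can add transfusions.

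**What dilution means here.** Let r_M and r_R be reaction rates per MIR and per conventional transfusion, and assume late units are conventional and reactions are equally well reported.

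- Per transfusion, the MIR column averages (1 - f)r_M + f r_R and the REF column r_R. The difference is (1 - f)(r_M - r_R), so it shrinks by f, about 17% to 25%. The excess of the ratio over 1 shrinks by the same fraction.
- In mean events over one subject from each sequence, the columns hold 2n r_M + k r_R and 2n r_R + k r_R. The difference, 2n(r_M - r_R), is unchanged; the late events only add noise.

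**Late events are not purely non-study.** Mean linear survival of Mirasol-treated cells was 60.49 days in healthy volunteers (Protocol 5.2). If they decline linearly to zero, the share of surviving cells from the last MIR transfusion still present at the EOT visit is 1 - 14/60.49 = 77% down to 1 - 28/60.49 = 54%. A delayed MIR effect can therefore first appear after the EOT visit.

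**The case against.** **REF is standard inventory.** Protocol 10.2 and 13.2 draw REF units from routine stock, so late standard-of-care units are ordinarily the same kind of blood. In the MIR-then-REF sequence, late events follow conventional blood and are filed under conventional blood. This stands: a reader might infer that both columns are contaminated alike, but only the MIR column mixes products.

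**Exposure shares are not AE shares.** Study transfusions carry vital signs and samples at 15 minutes, Day 1 and Day 7 (Protocol 14.3), whereas late ones have no scheduled monitoring before the final visit. This also stands. It would be wrong to infer that 17% to 25% of MIR-column AEs are misfiled; the share of events is probably smaller.

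**The transfusions may be recorded anyway.** Protocol 14.3.1 asks for blood products throughout the study, and Protocol 10.3 and 13.3 set no end date for off-protocol units. However, 14.3.1 is a checklist for study transfusions and refers to Protocol 17, where the cut-off is explicit. Section 17 should be taken to govern.

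**Causality does not depend on the eCRF.** A reader might infer that late events cannot be assessed individually. The documents do not support that. Investigators have hospital and clinic records as source data (Protocol 22.2.1), the sponsor may request more information on SAEs (19.9.2), and the Research Monitor assesses SAE causality independently (19.12.1). The missing dates are an inconvenience rather than a loss of the evidence.

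**The limitation is disclosed, and the SAP is silent on the end of Period 2.** Both are true. The caveat produces no table or rule, though, and the SAP provides no other column for late events.

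**Conclusion.** The concern holds as a minor point about the safety tables. The AE window is misstated in Protocol 21.9.1 and SAP IX.A. Following the SAP as written puts events after the EOT visit under the Period 2 product, including MIR in the REF-then-MIR sequence.

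About 2 to 4 non-study transfusions fall in that window, making up roughly 17% to 25% of the episodes behind the MIR column. This can dilute a MIR-REF difference in reactions on a per-transfusion or ratio scale. The size rests on regular intervals, equal sequences, late units being conventional and, for the full dilution, equal ascertainment, which the lighter late monitoring makes unlikely.

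Two stronger conclusions should not be drawn. The primary endpoint is not affected, because it comes from the two episodes after each wash-in. Nor should late AEs be dropped from the main tables, since Mirasol-treated cells may still be circulating.

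**What to change.** 1. Correct Protocol 21.9.1 and SAP IX.A to say that AEs are recorded through the final visit or early termination, in line with Protocol 19.6.1.
2. In SAP IX.A, keep the all-TEAE tables and add one table, by product, of TEAEs and adverse transfusion reactions split by onset up to versus after the EOT visit. State how an onset on the EOT day is classed when a standard-of-care transfusion is given that day; for example, keep it in the earlier group and list it individually.

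The split uses AE onset and visit dates already collected. The cost is one extra safety table and wording changes. The SAP change should be made before database lock under SAP I.B; the Protocol correction follows the IRB/EC route in Protocol 22.4.1.

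Optionally, the next protocol amendment could extend blood-product recording (date and type) to the final visit, about 2 to 4 entries per subject on an existing page. It needs IRB/EC approval and adds little beyond the split table, so it does not justify an amendment of its own.

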18 INVESTIGATIONAL DEVICE

18.1 Device Deficiencies

All device deficiencies involving any device component must be reported to the Sponsor within 24 hours upon knowledge of the event. The Device Deficiency Report Form (located in the study MOP) will be used for reporting. Every attempt should be made by the investigational site to save or collect the defective device, and if appropriate, the packaging, for return to the Sponsor. If the deficiency occurs with the Illuminator, a service technician from the Sponsor will evaluate and determine whether service or replacement is necessary. A qualified Sponsor representative will investigate and determine root cause and corrective actions as applicable, and directives will be provided to the site if warranted.

Examples of device deficiencies warranting reporting to the Sponsor include the following:

- Any situation where the device or accessory to the device physically breaks for any reason.
- Any situation where a component of the device or the disposables kit fails to perform as it is specified in the study CIP or Blood Processing and Storage Guidelines.
- Potential manufacturing or shipping failures where device contamination, potential for device contamination, or a break in sterility or sterile barrier upon opening the device packaging is identified.

18.2 Receipt, Storage, Accountability

The investigational devices and accessories will be received, stored, and accounted for at the Blood Centers.

18.2.1 Receipt of Study Device

The contents should be examined upon receipt to ensure that packaging and labeling is intact and the devices have not been damaged. Potential damages must be reported to the Sponsor.

18.2.2 Storage

The devices should be stored in a cool, dry place. Devices should be with their original shipping materials. Proper care should be taken to ensure that the devices will not be damaged.

18.2.3 Accountability

The Investigator or designated site staff must maintain accountability records throughout the course of the study. The Clinical Research Associate (CRA) will review inventory and accountability of disposables and study supplies during monitoring visits.

The Investigator will not supply medical device materials to other Investigators who are not participating in the study. Device use, other than as directed by this CIP, is not allowed without prior authorization from the Sponsor.

Used materials are to be handled as per the study site's standard procedures. At the conclusion of the study, unused materials will be returned to the Sponsor/designee.

19 ADVERSE EVENTS/EFFECTS

19.1 Potential Transfusion Risks

Blood component transfusion is a common and usually safe procedure. However, even with advanced donor screening and other safety mitigation strategies employed, adverse transfusion reactions may still occur. It has been estimated that 5%-6% of all transfusion recipients experience adverse reactions from transfusion of blood or blood products.⁴² Transfusion-related adverse reactions may include nausea, chills, fever, urticaria, hives, itching, bronchospasm, hemoglobinuria, dyspnea, hypoxia, hypotension, tachycardia, transfusion-associated circulatory overload, bacterial and/or viral contamination, allergic transfusion reaction, anaphylaxis, acute lung injury, hemolytic transfusion reaction, nonimmunologic hemolysis, alloimmunization, iron overload, and sepsis. Transfusion-related adverse reactions may be classified by temporal relationship to the transfusion (ie, immediate, delayed) or by relationship to immunological factors.^{42,43}

Transfusion-related adverse reactions are summarized in Table 19-1. Notably, these adverse reactions are general blood transfusion risks and are not specific to Mirasol System treatment.

